#### **9.4. Heart Rate, Weight, and Height**

Heart rate is collected at Baseline and the Month 6, 12, 18, 24, 30, 36, 42, and 48 visits. Weight and height are collected at Baseline and the Month 12, 24, 36, and 48 visits.

Observed values at each visit and changes from study Baseline to each post-baseline visit will be summarized by stage, visit and treatment group using descriptive statistics.

Heart rate will be provided in subject data listings.

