#### 3.3. Brief Description

This will be a 3-arm randomized, multicenter, double-masked, placebo-controlled, Phase 3 study conducted in 2 stages. Stage 1 is a safety and efficacy phase of 3 years (36 months) in duration, during which subjects will be allocated one of three study medications. Stage 2 is a randomized cross-over phase of 1 year (12 months) in duration, for the purpose of observing the effects of changing or stopping treatment. During Stage 2, subjects will be re-randomized to receive 1 of the 3 study medications with subjects initially randomized to Vehicle only eligible for randomization to 0.01% or 0.02% Atropine Sulfate Ophthalmic Solution. Subjects (aged 3 to  $\leq$  17.0 years) will enter the study with myopia spherical equivalent refraction (SER) of at least -0.50 D and no greater than -6.00 D myopia in each eye as measured by cycloplegic autorefraction and following successful eligibility screening at the Screening/Baseline visit will be randomized to one of the 3 treatment groups in a 2:2:3 ratio. The randomization will be stratified twice: (1) by age at randomization (subjects < 9 years; subjects  $\geq$  9 years) and by (2) refractive error (less myopic: SER -0.50 to -3.00 D; more myopic: one or more eyes with SER -3.01 to -6.00 D). The stratification is used to balance these characteristics across the 3 treatment groups.

The target number of subjects to be randomized into the 6-year to 10-year age group (436), the primary efficacy population. Approximately 483 subjects over all eligible ages will be enrolled. Enrollment will proceed until 436 subjects aged 6 to 10 years have been randomized and at least 483 subjects overall have been randomized. Enrollment may be closed to subjects age  $\geq$  11 years following enrollment of 50 subjects in this age group to avoid over-enrollment into the study.

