### 6.2. Key Definitions

Treatment-emergent adverse events (TEAEs) of Stage 1 are defined as any new or worsening of existing adverse events that occur or worsen between the first dose date of Stage 1 and the last dose date of Stage 1.

TEAEs of Stage 2 are defined as any AE the occurs or worsens between the first dose date of Stage 2 and the last dose date of Stage 2.

First dose date for Stage 1 is defined as the first dose of study medication received after randomization in Stage 1.

First dose date for Stage 2 is defined as the first dose of study medication received after the Stage 1 last dose date and subject is re-randomized.

For subjects who did not receive study medication in a given stage, leave first dose date for that stage as missing. If the first dose date is missing and if the subject is randomized, impute the missing first dose date using the randomization date in the analysis of Time to Change from Baseline in Myopia Progression of -0.75D (see 8.3.7 and 8.3.8).

Baseline for Stage 1 is defined as the last measurement prior to first dose of study medication in Stage 1, If an adverse event starts or non-study medication taken on the day of first dose it will be treated as occurring after treatment started. All other planned measurements are presumed to occur prior to first dose of study medication.

Baseline for Stage 2 will be defined as latest results prior to start of study medication in Stage 2, which occurs the day after the Month 36 visit. The results of the Month 36 visit will act as the baseline for Stage 2.

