## 8. Efficacy

The primary and all secondary endpoints comprise a fixed sequence set of endpoints to be tested in the order given below. All statistical testing will be performed using a two-sided testing procedure with  $\alpha=0.05$ . Summaries of change for Stage 2 will include change from baseline and change from Stage 2 baseline (Month 36).

The order for the fixed sequence of endpoints to be tested are:

1. Between-treatment group (Atropine Sulfate Ophthalmic Solution, 0.02% versus Vehicle) difference in the proportion of subjects' eyes who show less than 0.5 D myopia progression (SER) from baseline at the Month 36 visit. (Primary Endpoint)
2. Between-treatment group (Atropine Sulfate Ophthalmic Solution, 0.02% versus Vehicle) difference in the mean change from baseline in SER at the Month 36 visit.
3. Between-treatment group (Atropine Sulfate Ophthalmic Solution, 0.01% versus Vehicle) difference in the proportion of subjects' eyes who show less than 0.5 D myopia progression (SER) from baseline at the Month 36 visits.
4. Between-treatment group (Atropine Sulfate Ophthalmic Solution, 0.01% versus Vehicle) difference in the mean change from baseline in SER at the Month 36 visit.
5. Between-treatment group (Atropine Sulfate Ophthalmic Solution 0.02% versus Vehicle) difference in the mean change from baseline in axial length at the Month 36) visit,
6. Between-treatment group (Atropine Sulfate Ophthalmic Solution 0.01% versus Vehicle) difference in the mean change from baseline in axial length at the Month 36 visit.

Not all sites used the same Vertex distance (VD) in mm when measuring refraction with autorefractor. All averaged SER measurements for each participant used in tables and analyses will be normalized to a VD of 0 mm to the corneal plane. The normalization (Fannin 1987) will be applied using

$$\text{Normalized SER} = \frac{100}{\frac{100}{\text{SER}} - \frac{\text{VD}}{10}}$$

where SER is the original SER from CRF.

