## 9. Safety

The population used for safety analyses will be the Safety Set (SS). Safety will be assessed on the basis of ophthalmic safety assessments (BCVA, photopic pupil size, slit-lamp examination (SLE), dilated fundus examination, and tonometry), HR, and adverse events (AE). Safety Tables will be provided separately for each stage of the study.

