#### **9.6. Photopic Pupil Size**

Photopic pupil size (mm) is collected at Baseline and the Month 6, 12, 18, 24, 30, 36, 42, and 48 visits. Photopic pupil size will be provided for each eye individually.

This document is confidential.

Observed values at each visit and changes from Baseline to each post-baseline visit will be summarized by stage, visit and treatment group using descriptive statistics. For Stage 2, the Stage 2 baseline (Month 36) will be used for the change from baseline calculation.

Photopic pupil size will be provided in subject data listings.

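### The Stage 2 heart-rate summary gives change only from study Baseline; add change from Month 36, shown by treatment sequence, so that the shift across the switch can be seen

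*SAP*

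**What the plan says.** SAP 9.4 gives heart rate, weight and height a single rule: besides the observed values, "changes from study Baseline to each post-baseline visit will be summarized by stage, visit and treatment group". It adds nothing for Stage 2. The same section confirms that the pre-switch value exists: "Heart rate is collected at Baseline and the Month 6, 12, 18, 24, 30, 36, 42, and 48 visits".

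The three ocular measurements summarized as change are treated differently. SAP 9.6, on pupil size, reads "For Stage 2, the Stage 2 baseline (Month 36) will be used for the change from baseline calculation", and SAP 9.5 (visual acuity) and 9.9 (intraocular pressure) carry the same sentence. The general definition in SAP 6.2 agrees with them: "The results of the Month 36 visit will act as the baseline for Stage 2".

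A rule that reports Stage 2 change from both baselines does exist, but it is in SAP 8 (Efficacy). Heart rate belongs to SAP 9, which adds that "Safety Tables will be provided separately for each stage of the study". The table concerned is 14.3.4.2.2, in the Stage 2 Safety Set. SAP 5.2 groups that set by the first treatment received within the stage, and uses the treatment sequence only where data from both stages are shown together.

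SAP 3.3 describes Stage 2 as "for the purpose of observing the effects of changing or stopping treatment".

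**The concern.** Heart rate is the scheduled measurement closest to a systemic antimuscarinic effect. The protocol's Data and Safety Monitoring Plan names it first among the parameters to be watched, and SAP Table 3 lists an increase in heart rate among the antimuscarinic events. A stage designed to show what happens when treatment is changed or stopped should report each child's change from the last value before the switch. That value is collected at Month 36, but the planned table does not use it as a reference. Its reference is a measurement taken before any study drug, three years before re-randomization.

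At stake is how readable one safety table is. A reader who wants to know whether heart rate rose on starting atropine, or fell on stopping it, would not find that change or its spread there.

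**Working it through.** **1. Length of the change interval.** Scheduled days are from SAP Table 1: Baseline 1, Month 36 = 1096, Month 42 = 1278, Month 48 = 1461.

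- From study Baseline: (1278 − 1)/365.25 = 3.50 years; (1461 − 1)/365.25 = 4.00 years.
- From Month 36: (1278 − 1096)/365.25 = 0.50 years; (1461 − 1096)/365.25 = 1.00 year.

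**2. What each change estimates.** The documents give no heart-rate figures, so the structure is set out in symbols. Let g be the age drift in bpm per year and e the atropine effect while on drug. Assume no carry-over and, for simplicity, the same e for both concentrations. Expected change = drift × years + effect at the visit − effect at the reference. Study Baseline precedes dosing, so the effect there is zero. At Month 48:

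| Sequence | From study Baseline | From Month 36 |
|---|---|---|
| Vehicle to atropine (start) | 4g + e | g + e |
| Atropine, same dose (continue) | 4g + e | g |
| Atropine to Vehicle (stop) | 4g | g − e |

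In the first column, starting and continuing are identical and the stopping row contains no drug term. In the second column, starters and continuers differ by e, and the fall on stopping appears directly.

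As an illustration only, g = −2 and e = +4 give −4, −4 and −8 bpm from study Baseline, against +2, −2 and −6 bpm from Month 36. The identity of the first two rows in the study-Baseline column holds for any g and e. Over an assumed drift of 0 to −3 bpm per year, the age part is 0 to −12 bpm from study Baseline and 0 to −3 bpm from Month 36.

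**3. Who is in each Stage 2 arm.** Planned Stage 1 numbers are 138 Vehicle, 138 on 0.01% and 207 on 0.02%. Re-randomization is 1:1 for Stage 1 Vehicle and 1:1:1 for Stage 1 atropine (SAP 3.6).

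- Each Stage 2 atropine arm: 138/2 + 138/3 + 207/3 = 69 + 46 + 69 = 184. Starters from Vehicle are 69/184 = 37.5%; the other 62.5% came from 0.01% (25%) or 0.02% (37.5%).
- Stage 2 Vehicle arm: 46 + 69 = 115, all of whom stopped atropine.

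Dropout that is equal across arms leaves these shares unchanged.

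**4. Replacing the baseline in the pooled table.** With the same illustration:

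- Study Baseline: atropine −4, Vehicle −8, difference 4, which is e.
- Month 36: atropine 0.375 × (+2) + 0.625 × (−2) = −0.5; Vehicle −6; difference 5.5, which is 1.375e.

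So the Month 36 change isolates the switch only when it is shown by sequence.

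**5. Precision.** With SD s at each visit and correlation ρ, the variance of change is 2s²(1 − ρ). The ratio, Month 36 to study Baseline, is (1 − ρ₃₆)/(1 − ρ₀). Assume ρ₀ of 0.3 to 0.5 over 3.5 to 4 years and ρ₃₆ of 0.5 to 0.7 over 6 to 12 months.

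- Least gain (ρ₀ = 0.5, ρ₃₆ = 0.5): 0.5/0.5 = 1.00, so 0% lower.
- Greatest gain (ρ₀ = 0.3, ρ₃₆ = 0.7): 0.3/0.7 = 0.43, so 57% lower.

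**The case against.** The best defence is that study Baseline is a legitimate reference and that little is lost. It is untreated for every child, so change from it answers a fair safety question: how far is this child from the drug-free state? The wording of SAP 9.4 is explicit and may be deliberate. Re-randomization keeps contrasts between arms with the same Stage 1 treatment unbiased under either reference, and a drift common to concurrent arms cancels. Observed values are summarized by visit, and for children with both values the difference in observed means equals the mean change. At a correlation of 0.5 the SD of change from Month 36 equals the SD of a single reading, since √(2 × 0.5) = 1, so there would be no gain over the observed-value summary. Heart rate is also listed by subject, and antimuscarinic adverse events have their own Stage 2 table.

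Most of this stands, and it limits the point. It does not supply the paired change and its spread, which an unpaired reading of visit means cannot give. Nor does it explain why heart rate differs from the three ocular measures.

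Three stronger readings are tempting, and the documents do not support them:

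- A reader might infer that the study-Baseline change mixes the Stage 1 drug with the Stage 2 switch. Study Baseline is drug-free, so Stage 1 drug enters only through carry-over, which nothing in the documents establishes. Month 36 is the reference that includes it, because 345 of 483 planned subjects (138 + 207, or 71%) were assigned atropine in Stage 1.
- A reader might infer that the age trend dominates the change. That depends on an assumed drift.
- A reader might infer that Month 36 should simply replace study Baseline. In a table pooled by Stage 2 treatment, that would distort the arm contrast (step 4 of the working).

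**Conclusion.** The point holds as a minor improvement. SAP 9.4 plans no within-subject heart-rate change across the Stage 2 switch, although the reference value is collected and SAP 9.5, 9.6 and 9.9 use it for other measures. If there is no carry-over, the planned change cannot tell starters from continuers at the same dose, and it does not show a reversible fall on stopping. This follows from the choice of reference and needs no heart-rate figures.

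The information is blurred, not lost, since observed values by visit still allow an unpaired comparison. The summary is descriptive, and no test, error rate or Stage 1 conclusion depends on it. The size of any precision gain is not known: 0 to 57% lower variance under the assumed correlations. A single narrow figure within that range would rest on selected values.

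**What to change.** In SAP 9.4, state that for Stage 2 the heart-rate change is summarized from the Month 36 value as well as from study Baseline. Show both in Table 14.3.4.2.2 by Stage 1 to Stage 2 treatment sequence, using the eight groups already listed in SAP 8.4. The display by sequence is part of the fix, because the Stage 2 atropine arms pool starters, continuers and dose-switchers. Keep study Baseline for height and weight.

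No new data or visits are needed. The cost is a sentence or two in the SAP and extra rows or columns in one table, with small groups. On planned numbers with the protocol's 27% Stage 1 drop-out, taken as equal across arms, each sequence would hold about 34 to 50 children (138 × 0.73/3 = 34; 138 × 0.73/2 = 50; 207 × 0.73/3 = 50).

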#### **9.5. Monocular Best-Corrected Visual Acuity (BCVA)**

Monocular Best-Corrected Visual Acuity (BCVA) is performed at Baseline and the Month 6, 12, 18, 24, 30, 36, 42, and 48 visits. BCVA will be provided as LogMar BCVA for both distance and near for each eye.

Observed values at each visit and changes from Baseline to each post-baseline visit will be summarized by stage, visit and treatment group using descriptive statistics. For Stage 2, the Stage 2 baseline (Month 36) will be used for the change from baseline calculation. Changes that warranted a new prescription will also be identified.

Monocular Best-Corrected Visual Acuity will be provided in subject data listings.

#### **9.6. Photopic Pupil Size**

Photopic pupil size (mm) is collected at Baseline and the Month 6, 12, 18, 24, 30, 36, 42, and 48 visits. Photopic pupil size will be provided for each eye individually.

This document is confidential.

Observed values at each visit and changes from Baseline to each post-baseline visit will be summarized by stage, visit and treatment group using descriptive statistics. For Stage 2, the Stage 2 baseline (Month 36) will be used for the change from baseline calculation.

Photopic pupil size will be provided in subject data listings.

#### **9.7. Slit Lamp Examination**

A slit lamp exam is performed at Baseline and the Month 6, 12, 18, 24, 30, 36, 42, and 48 visits. Assessments of conjunctiva, cornea, anterior chamber, iris, lens, and lids will be provided for each eye individually.

Findings at each visit will be summarized by stage, visit and treatment group using descriptive statistics.

Slit lamp exam results will be provided in subject data listings.

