# Withdrawal of Subjects:

All subjects randomized into the study will be encouraged to complete all study assessments through the Month 48 Visit (End of Study), including subjects that cannot or do not wish to continue study treatment (withdraw consent/assent from study treatment but are willing to continue study visits).

The following are the criteria for considering withdrawal from the study (Study discontinuation prior to Visit Month 48):

- Withdrawal of subject consent/assent to continue with study visits.
- If the site and/or the overall study is terminated for any reason.
- The Investigator considers it is in the best interest for the subject to leave the study. This may include the development of damage to the cornea (Section 8.5 Discontinuation of Study Medication).

If a subject withdraws from the study, the reason for the subject's withdrawal will be recorded in the electronic case report form (eCRF).

If a subject is discontinued from study medication before the Month 48 visit, then all Month 48 procedures should be performed at the visit the subject discontinues study medication. The subject should continue in the study off study medication. Subjects should be encouraged to return for the 6 Month interval visits; however, returning for the 12 Month interval visits is essential. Subjects discontinuing study medication prior to Month 36 would continue to be seen for scheduled visits (at 6 Month or 12 Month intervals as noted above) until they reach the Month 36 interval.

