#### **9.9. Intraocular Pressure**

Intraocular pressure (mmHg) is measured at Baseline and the Month 6, 12, 18, 24, 30, 36, 42, and 48 visits. Measurement of intraocular pressure will be provided for each eye individually.

Observed values at each visit and changes from Baseline to each post-baseline visit will be summarized by stage, visit and treatment group using descriptive statistics. For Stage 2, the Stage 2 baseline (Month 36) will be used for the change from baseline calculation.

Intraocular pressure measurements will be provided in subject data listings.

This document is confidential.

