	14.3.2.4.3	Listing of Non-Ocular Treatment-Emergent Adverse Events Leading to Withdrawal from Study	Safety Set
14.3.3	Not to be used for any Tables	Narratives of Deaths, Other Serious, and Certain Other Significant Adverse Events ( NOTE: this section is for Medical Writing narratives only, normally not completed by Syneos Health Biostatistics. No tables should go here. ).	
14.3.4		Abnormal Laboratory Value (each subject)	
14.3.4.1		Ophthalmic Safety Assessment Data	
	14.3.4.1.1.1	Monocular Best-Corrected Visual Acuity Results – Stage 1	Stage 1 Safety Set
	14.3.4.1.1.2	Monocular Best-Corrected Visual Acuity Results – Stage 2	Stage 2 Safety Set
	14.3.4.1.2.1	Pupil Size (mm) – Stage 1	Stage 1 Safety Set
	14.3.4.1.2.2	Pupil Size (mm) – Stage 2	Stage 2 Safety Set
	14.3.4.1.3.1	Slit Lamp Examination Results – Stage 1	Stage 1 Safety Set
	14.3.4.1.3.2	Slit Lamp Examination Results – Stage 2	Stage 2 Safety Set
	14.3.4.1.4.1	Dilated Fundus Examination Results – Stage 1	Stage 1 Safety Set
	14.3.4.1.4.2	Dilated Fundus Examination Results – Stage 2	Stage 2 Safety Set
	14.3.4.1.5.1	Tonometry - Intraocular Pressure (mmHg) – Stage 1	Stage 1 Safety Set
	14.3.4.1.5.2	Tonometry - Intraocular Pressure (mmHg) – Stage 2	Stage 2 Safety Set
14.3.4.2		Vital Signs and Physical Findings	
	14.3.4.2.1	Vital Signs and Physical Findings – Stage 1	Stage 1 Safety Set
	14.3.4.2.2	Vital Signs and Physical Findings – Stage 2	Stage 2 Safety Set
14.3.4.3		Quality of Life	
	14.3.4.3.1	Modified Amblyopia Treatment Index (mATI)	Stage 2 Safety Set

This document is confidential.

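### The slit-lamp and fundus tables report findings visit by visit with no within-child or within-eye comparison with baseline, so they cannot count new or worsened findings by arm

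*SAP*

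**What the plan says.** SAP 9.7 sets the schedule: "A slit lamp exam is performed at Baseline and the Month 6, 12, 18, 24, 30, 36, 42, and 48 visits". It then gives its only analysis rule, "Findings at each visit will be summarized by stage, visit and treatment group using descriptive statistics", and promises subject listings. SAP 9.8 uses the same rule for the dilated fundus exam, which is done at Baseline and Months 12, 24, 36 and 48.

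The neighbouring continuous measures are treated differently. For pupil size SAP 9.6 says "Observed values at each visit and changes from Baseline to each post-baseline visit will be summarized by stage, visit and treatment group", and SAP 9.5 (BCVA) and 9.9 (intraocular pressure) match it. All three add a Stage 2 rule: "For Stage 2, the Stage 2 baseline (Month 36) will be used for the change from baseline calculation".

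The SAP Index of Tables has one results table per exam per stage, such as "Slit Lamp Examination Results – Stage 1". It lists no shift table and no worst-post-baseline table for either exam.

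Both exams are named safety variables in the Protocol (Criteria for Evaluation) and in SAP 9. Under Withdrawal of Subjects, the Protocol lets the investigator judge that leaving the study is in the child's best interest, and adds: "This may include the development of damage to the cornea".

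**The concern.** The safety question is how many children on each arm developed something they did not have before, or had something get worse. A by-visit table reports prevalence. A lid, conjunctival, lens or retinal finding that was there before the first drop is counted again at every exam, and a new finding that has resolved by the next exam is counted once.

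Stage 2 raises a second problem. Children are re-randomized at Month 36, and a Stage 2 row does not tell a finding brought over from Stage 1 treatment from one that began on the Stage 2 treatment.

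The third problem is which exams reach the table. SAP 6.4 keeps one visit per window, and an exam prompted by symptoms or by stopping treatment need not be the one kept.

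**Working it through.** **1. Plan's own figure.** The Protocol expects 27% drop-out over Stage 1, about 10% a year: 1 − 0.9³ = 0.271. On 0.02%, 207 × 0.73 = 151.1, which reproduces the stated minimum of 150. On Vehicle, 138 × 0.73 = 100.7. SAP 13.2.5.2 takes percentages over subjects with an observation. The Month 36 rows would therefore rest on about 151 and 101 children, with about 56 and 37 outside them.

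**2. Why a Baseline row is not enough.** Let b be the baseline prevalence, r the share of those findings that resolve, and i the risk of a new finding in children clear at baseline. A later row shows b(1 − r) + (1 − b)i. Knowing b and the row does not determine i. Take 100 children, 10 with a finding at Baseline and 10 later. They may be the same 10 (i = 0), or 5 of them plus 5 new cases among the 90 who were clear (i = 5.6%). The table looks the same either way.

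**3. Windowing.** SAP Table 1 gives Month 12 a window of Day 274 to 456, scheduled at Day 365. Suppose a child has the scheduled exam on Day 366 and an early-termination exam on Day 440. The distances are 1 and 75 days, so the Day 366 exam is summarized. If the child then leaves the study, the Day 440 exam appears in no row.

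**4. Masking (illustration; all rates assumed).** New-finding risk is 8% on 0.02% (n = 207) and 2% on Vehicle (n = 138), with r = 0 and no drop-out on either side. The visit row is b + (1 − b)i. The new-finding count uses 207(1 − b) and 138(1 − b) children. Power is the two-sided 5% normal approximation for two proportions. The plan tests nothing here, so power only measures how well each table could separate the arms.

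| b | Visit row, 0.02% v Vehicle | Power, visit row | Power, new findings (8% v 2%) |
|---|---|---|---|
| 0% | 8.0% v 2.0% | 68% | 68% |
| 5% | 12.6% v 6.9% | 39% | 66% |
| 10% | 17.2% v 11.8% | 27% | 63% |
| 20% | 26.4% v 21.6% | 17% | 57% |
| 30% | 35.6% v 31.4% | 12% | 51% |

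If half the baseline findings resolve (r = 0.5), visit-row power at b = 10% is 37%.

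**5. Counting over all Stage 1 exams (illustration).** With a per-exam risk i of 2% on 0.02% and 1% on Vehicle, the share ever affected is 1 − (1 − i)^k. The unpooled z is the difference divided by √[p₁(1 − p₁)/207 + p₀(1 − p₀)/138].

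- Slit lamp, k = 6: 11.4% v 5.9%, z about 1.9.
- Fundus, k = 3 because it is yearly: 5.9% v 3.0%, z about 1.3.
- With 10% loss a year, summing 0.9^t × i(1 − i)^(j − 1) over exams j at year t: slit lamp 9.6% v 4.9%, z about 1.7; fundus 4.8% v 2.4%, z about 1.2.

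**6. Study withdrawal (illustration).** If 2, 4, 6 or 10 of 207 children develop a finding and all leave before Month 36, the Month 36 row shows 0 of 151. A worst-post-baseline count shows 1.0%, 1.9%, 2.9% or 4.8%.

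**The case against.** Much of the case for leaving the plan alone is sound, and it rules out three stronger readings.

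- **A reader might infer that there is no baseline reference at all.** That is not so. Baseline is one of the listed exam visits, so a group-level Baseline row is covered, and SAP 6.2 makes the Month 36 results the Stage 2 baseline for the whole plan. What is missing is the comparison within a child or eye.
- **A reader might infer that a child withdrawn for corneal damage vanishes from the report.** The documents do not support this. A child who stops medication has end-of-study procedures at that visit, including both exams, and is meant to stay in follow-up off drug. Only leaving the study empties later rows, which is true of any by-visit table, including those for pressure and pupil size. The exam stays in the listings, and SAP 9.3 tabulates ocular TEAEs leading to withdrawal and to drug discontinuation. Significant or severe corneal damage is excluded at entry, so pre-existing damage of that grade cannot hide new damage. Masking concerns milder findings and other structures.
- **A reader might set one Month 36 row beside the pooled three-year count.** With 5% baseline prevalence and the rates in step 5, that row is 7% v 6%, z about 0.3, against z about 1.9. The arithmetic is right but the comparison is not like for like. It sets one exam against six, applies drop-out to the row only, and uses an exam count that does not fit the fundus schedule.

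The strongest remaining argument is that TEAEs are defined as new or worsening and counted once per child per term, which is already an incidence measure. That holds for findings reported as adverse events. But the supplied text does not say that a new exam finding must be reported as one, and the Protocol section cited on discontinuation is not in the supplied text. TEAEs also stop at the last dose date, so a finding dated after it falls outside. The share of exam findings that the adverse event tables miss is unknown; it cannot be taken as zero.

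Listings, and treatment sequence in displays that span both stages (SAP 5.2), allow an individual case to be traced. They give no comparison between arms.

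**Conclusion.** The point holds in this limited form. As written, SAP 9.7 and 9.8 cannot deliver a count of children with a new or worsened slit-lamp or fundus finding by arm, cannot separate Stage 1 carry-over from Stage 2 onset, and may leave an early-termination or unscheduled exam out of the summary. These conclusions follow from the text and need no assumed rate.

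The size cannot be settled from the documents, which give no baseline prevalence, resolution rate or incidence. In the like-for-like illustration, with no resolution, the loss of power ranges from nil at zero baseline prevalence to 51% falling to 12% at 30%. Those figures depend wholly on the assumed 8% and 2% and on all 207 and 138 children being examined.

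No primary or secondary efficacy analysis is affected. This is a safety-reporting gap that should be closed; it does not undermine the trial.

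**What to change.** In SAP 9.7 and 9.8, and in the Index of Tables:

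- For each structure, add by-eye and by-subject shift tables from Stage 1 baseline to each visit and to the worst post-baseline result. Let the worst result draw on every exam, including unscheduled and early-termination ones that the windowing rule would set aside.
- Report by arm the number and percentage of children with at least one new or worsened finding in either eye, stating the denominator.
- For Stage 2, do the same from Month 36 by treatment sequence, so that carried-over findings are shown apart from new ones.
- Keep the by-visit tables as supporting displays.

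The cost is one derived flag and one extra table per exam per stage, from data already collected. If a magnitude is quoted in support, label it as illustration and use three post-baseline Stage 1 exams for the fundus, not six.
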